## **4 Study Population and Duration of Participation**

Adult subjects, ages 30-65, who are interested in rhytid treatment of the glabella with a neuromodulator under FDA approved use. Each participant will participate for 180 days.

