### ***3.4 Study Endpoints***

#### **3.4.1 Primary Study Endpoint**

The primary endpoint is to quantify the change in dynamic strain of the glabella area after injection of four neuromodulators using 3D facial imaging measurements over time.

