### ***4.1 Duration of Study Participation***

The duration of study participation is a minimum of 180 days. Subjects will receive injections on day-1, and follow up imaging and analysis occurs on day 3, 30, 90 and 180 post intervention.

The overall study duration is estimated 12- 18 months. It may take approximately 6 months to enroll all subjects and complete initial imaging and procedures, 7 months for follow up imaging, and 4-5 months for data analysis. Each individual subject's participation time in the study will consist of the duration of the initial imaging session (approximately 20 minutes), procedure (15 minutes), follow up imaging (20 min).

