### **4.4 Exclusion Criteria**

- Females under 30 or above 65 years of age
- Males

CONFIDENTIAL

- Those who have received glabellar injections for rhytids <12 months
- Underwent cosmetic surgical procedure above the malar region
- Those with a condition that affects facial expression, such as prior stroke

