### AbobotulinumtoxinA (Dysport)

Reconstitute 300 unit vials with 3.0 mL preservative-free 0.9% sodium chloride injection, USP. Load 0.5mL in a single syringe with a 30-gauge needle. Each of the five FDA approved glabella injection points will receive 0.1mL of the reconstituted solution (10 units of toxin) intramuscularly for a total of 50 units in 0.5mL.

Once reconstituted, unused toxin may be stored in the original container in a refrigerator at 2-8°C or 36-46°F. Do NOT freeze. All toxin must be discarded within 24 hours after reconstitution. All reconstituted vials should be single-use for one subject only.

### 5.2.2 Visit 2

Visit 2 which will occur 3-days post-injection, will consist of a repeat of the above measurements using 3D imaging with facial animations of 1) relaxed and 2) frowning. Subjects will also complete the FACE-Q via electronic REDCap survey and communicate any questions or concerns.

### 5.2.3 Visit 3

Visit 3 which will occur 30-days post-injection, will consist of a repeat of the above measurements using 3D imaging with facial animations of 1) relaxed and 2) frowning. Subjects will also complete the FACE-Q via electronic REDCap survey and communicate any questions or concerns.

#### 5.2.4 Visit 4

Visit 4 which will occur 90-days post-injection, will consist of a repeat of the above measurements using 3D imaging with facial animations of 1) relaxed and 2) frowning. Subjects will also complete the FACE-Q via electronic REDCap survey and communicate any questions or concerns.

#### 5.2.5 End of Study Visit 5

Visit 5 which will occur 180-days post-injection, will consist of a repeat of the above measurements using 3D imaging with facial animations of 1) relaxed and 2) frowning. Subjects will also complete the FACE-Q via electronic REDCap survey and communicate any questions or concerns.

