**TABLE 1 SCHEDULE OF STUDY PROCEDURES**

	Baseline Visit 1	Intervention	Follow-up Visit 2 Day 3	Follow-up Visit 3 Day 30	Follow-up Visit 4 Day 90	Follow-up Visit 5 Day 180
Visit Window	Day 1	Day 1	Day 3 ±1	Day 30 ± 5	Day 90 ±7	Day 180 ±10
Eligibility	X					
Informed Consent	X					
Demographic	X					
Medical History	X					
Consultation	X					
Vectra Photography		X	X	X	X	X
FACE-Q		X	X	X	X	X
Adverse Events	X	X	X	X	X	X

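### Strain is followed to Day 180, but no planned step asks about neuromodulator or upper-face treatment after the study injection, so such treatment will not be systematically identified behind late values

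*Combined protocol and SAP*

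**What the plan says.** Section 3.4.1 sets the primary endpoint as to "quantify the change in dynamic strain of the glabella area after injection of four neuromodulators using 3D facial imaging measurements over time". It names no single time point, so every visit contributes. Section 4 states "Each participant will participate for 180 days", and Section 4.1 adds that "follow up imaging and analysis occurs on day 3, 30, 90 and 180 post intervention".

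At entry, Section 4.4 excludes "Those who have received glabellar injections for rhytids <12 months" and anyone who "Underwent cosmetic surgical procedure above the malar region". The Study Summary carries similar limits. All of these concern the time before the study injection.

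After injection, Sections 5.2.2 to 5.2.5 describe each visit as repeat imaging in two expressions, and then: "Subjects will also complete the FACE-Q via electronic REDCap survey and communicate any questions or concerns". In "TABLE 1 SCHEDULE OF STUDY PROCEDURES", medical history and consultation are marked at baseline only. The rows marked at follow-up visits are photography, FACE-Q and adverse events.

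The withdrawal text (Sections 5.4 and 5.4.1) and the statistical plan (Section 6) do not mention treatment received during follow-up. Section 7.7 takes source data mainly from the medical record, with case report forms for items not normally held there.

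**The concern.** The protocol controls neuromodulator exposure for 12 months before entry and does not ask about it during the 180 days in which the outcome is measured. The subjects want wrinkle treatment (Sections 4 and 4.3). They are recruited partly through a high-volume plastic surgery clinic (Section 4.5), and no text restricts other treatment during follow-up.

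A subject whose effect has faded has more reason to seek another injection than one whose effect persists. Her later strain and FACE-Q values would then be credited to the assigned product. If this happens more often in an arm whose product wears off sooner, that product looks more durable than it is, and the contrast between products shrinks or reverses. Randomisation does not prevent this, because the event comes after allocation and depends on the outcome. The results exposed are the late-visit comparison of products (Sections 2.1 and 3.4.2, item 1) and the correlation of FACE-Q with strain (Section 3.4.2, item 3).

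Analysts can choose how to handle a recorded event. They cannot reliably recover one that nobody asked about.

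**Working it through.** **1. Is the event captured anywhere?**

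- Visits 2 to 5 and Table 1: no question or row on treatment since injection.
- Section 7.2: specific questioning at each contact, but about adverse events, which Section 7.1.1 defines by symptoms, signs, illness or experience developing or worsening. An elective cosmetic injection would not ordinarily be reported under that definition.
- Section 7.4.1: concomitant medication appears once, as an example of content for a follow-up report on a serious adverse event.
- Section 7.7: the medical record could show treatment at the same institution, but no re-treatment field or extraction step is named.

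**2. Arm size.** Inputs: 140 subjects (Section 4.2), four equal arms (Section 3.2), 15% dropout (Section 6.1).

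- 140 × 0.85 = 119 evaluable; 119 / 4 = 29.75, about 30 per arm. In reverse, 119 / 0.85 = 140.
- This checks the dropout step only. The 140 itself cannot be reproduced, because the documents state no effect size, SD, significance level or power.

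**3. Shift in a between-arm contrast.** Assumptions not in the documents: re-treatment restores 1 SD of effect at Day 180; shares p1 (shorter-acting arm) and p2 (longer-acting arm) are re-treated. Shift = (p1 − p2) × 1 SD.

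- 10% versus 5%: 0.10 − 0.05 = 0.05 SD
- 20% versus 5%: 0.20 − 0.05 = 0.15 SD
- 30% versus 5%: 0.30 − 0.05 = 0.25 SD

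Standard error of a two-arm difference at 30 per arm: √(2/30) = 0.26 SD. The shifts are about 0.2, 0.6 and 1.0 standard errors.

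**4. The same problem as lost power.** Assume two-sided 5% significance, 80% power and 29.75 per arm. The detectable pairwise difference is (1.960 + 0.842) × √(2/29.75) = 0.726 SD. If a share c of the less durable arm is re-treated and then resembles the better arm, the difference becomes (1 − c) × 0.726.

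| c | Difference (SD) | Power | n per arm for 80% |
|---|---|---|---|
| 0 | 0.726 | 80.0% | 30 |
| 5% | 0.690 | 75.9% | 33 |
| 10% | 0.654 | 71.3% | 37 |
| 20% | 0.581 | 61.1% | 47 |
| 30% | 0.508 | 50.0% | 61 |

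**5. Within one arm.** Suppose 25% of the peak effect truly remains at Day 180 and re-treatment restores all of it. The observed share of peak is (1 − c) × 0.25 + c. At c = 20% this is 0.80 × 0.25 + 0.20 = 40%.

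**6. Does deleting the affected values cure it?** Worst case: normal outcomes, and re-treatment strikes the poorest responders first. Removing the lowest share p raises the arm mean by the normal density at that quantile divided by (1 − p).

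- p = 20%: 0.280 / 0.80 = 0.35 SD
- p = 5%: 0.103 / 0.95 = 0.11 SD
- Net: 0.35 − 0.11 = 0.24 SD in favour of the less durable arm, against 0.15 SD in step 3 with all values kept.

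Simple deletion can therefore do more harm than keeping the values.

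**The case against.** **Some events may surface anyway.** The medical record is the main source, recruitment is partly through the same clinic, and subjects can raise concerns at every visit. This stands. A reader might infer that re-treatment cannot be identified at all, and the documents do not support that. They support only that no planned step looks for it, so treatment elsewhere could be missed.

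**The forms are not in view.** The case report forms and consent pages are not in the text available. A question or an instruction to subjects could sit there. The gap shown is in the visit descriptions, Table 1 and Section 6.

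**Direction and size are assumed.** A reader might infer that the product ranking will be wrong. That requires re-treatment to occur, to differ by arm and to follow wearing-off, and the documents give no rate for any arm. Every shift in step 3 is below one standard error. This stands, although a shift of that kind is systematic and more subjects would not remove it.

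**Day 90 is less exposed.** Section 6.1 reports that the earlier study still found a significant strain reduction at day 90 for two products. A significant mean does not exclude fading in individuals, but the concern belongs mainly to Day 180. Day 3 is much less exposed.

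**The entry criteria give no rationale.** A reader might take them as an admission that such treatment distorts strain. Section 4.4 does not say so.

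**Setting values to missing needs a suitable model.** Section 6 names chi-squared, Fisher and paired t-tests, and the Study Summary adds linear regression. There is no repeated-measures between-arm model, and step 6 shows the risk of deleting values without one. This stands and limits the analysis part of the fix.

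**Conclusion.** The point holds as a gap in data capture. Followed as written, the plan measures strain and FACE-Q to Day 180 without asking whether the subject has since had a neuromodulator or an upper-face procedure, so such events will not be systematically identified.

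The bias is conditional. If subjects who fade sooner are re-treated more often, late values flatter the less durable product. Its size is unknown: 0.05 to 0.25 SD, against a standard error of about 0.26 SD, rests wholly on assumed rates and an assumed restored effect of 1 SD. The power figures rest on assumed rates, significance level and power as well, and are not forecasts.

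This should be corrected because asking is cheap at contacts that already take place, and recall collected after the study would be unreliable.

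**What to change.** - **Record.** Add one row to Table 1: at each follow-up visit, the date, type and area of any neuromodulator or upper-face procedure since the study injection, asked alongside the adverse-event questions of Section 7.2.
- **Report.** Give counts by arm.
- **Analyse.** In Section 6, present late-visit between-product strain and FACE-Q results twice, with all values and without values after such an event. State that exclusion can itself bias the comparison, because re-treatment depends on outcome. If a likelihood-based repeated-measures model is adopted, values after the event may be set to missing there.

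The cost is one form question and one extra sensitivity analysis. The change sets no rule on whether subjects may be treated; that remains with the investigators.

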### ***4.1 Duration of Study Participation***

The duration of study participation is a minimum of 180 days. Subjects will receive injections on day-1, and follow up imaging and analysis occurs on day 3, 30, 90 and 180 post intervention.

The overall study duration is estimated 12- 18 months. It may take approximately 6 months to enroll all subjects and complete initial imaging and procedures, 7 months for follow up imaging, and 4-5 months for data analysis. Each individual subject's participation time in the study will consist of the duration of the initial imaging session (approximately 20 minutes), procedure (15 minutes), follow up imaging (20 min).

### ***4.2 Total Number of Subjects and Sites***

140 patients will be enrolled from at a single location, the Hospital of the University of Pennsylvania.

### **4.3 Inclusion Criteria**

- Female
- 30-65 years of age
- Interested in glabellar injections to reduce rhytids and facial strain
- Participants must sign the informed consent form

### **4.4 Exclusion Criteria**

- Females under 30 or above 65 years of age
- Males

CONFIDENTIAL

- Those who have received glabellar injections for rhytids <12 months
- Underwent cosmetic surgical procedure above the malar region
- Those with a condition that affects facial expression, such as prior stroke

#### **4.5 Subject Recruitment**

Patients will be recruited through the plastic surgery clinic, which is a high-volume practice for those who may be interested in cosmetic injections. Additionally, we plan to use of a flyer posted throughout the health system and campus. Injections to the glabellar region to reduce rhytids are a popular procedure and we do not anticipate significant difficulty in recruiting willing participants.

#### **4.6 Vulnerable Populations:**

Children, pregnant women, fetuses, neonates, or prisoners are not included in this research study.

### **5 Study Procedures**

This section should list the procedures, observations, measures, etc. that will take place at each of the study visits. Every measure, procedure, observation, etc. that was listed in Section in Section 3.3 should be included in the study procedures section. A table can supplement this section. An example procedures table is included below in Appendix 15.1.

#### **5.1 Screening**

The screening visit involves patient evaluation of inclusion and exclusion criteria. This information is readily available on the intake visit and does not deviate from standard of care for a clinic visit, including age and past medical history. Once patients are deemed eligible, the process of informed consent will begin. Informed consent will take place.

#### **5.2 Study Intervention or Observational Phase**

Randomized Controlled Single Blinded Study

##### **5.2.1 Visit 1 (sometimes referred to as the baseline visit)**

Visit 1 involves screening, consent, baseline imaging to measure dynamic strain, randomization, intervention. The subject will be photographed using 3D imaging with multiple facial animations. All pre-procedure images will be evaluated for absolute strain performing two types of facial animation: 1) relaxed, 2) frowning. Following the baseline images, subjects will complete a FACE-Q questionnaire and then randomized to one of the four neuromodulators onabotulinumtoxinA (Botox, Allergan, Irvine, California), abobotulinumtoxinA (Dysport, Ipsen Biopharmaceuticals Inc. Cambridge, MA), incobotulinumtoxinA (Xeomin, Raleigh, NC) or PrabotulinumtoxinA (Jeuveau, Evolus, Newport Beach, California) according to a preset injection plan per FDA approved administration guidelines. The injector will be blinded to the neuromodulator assigned to the subject via randomization at the time of injection in order to decrease any underlying bias during drug administration. The syringes will be documented and prepared by appropriately trained staff.

CONFIDENTIAL

## Intervention Preparation as described on the FDA approved medication guide

### PrabotulinumtoxinA (Jeuveau)

[figure not shown]
Reconstitute 100 unit vials with 2.5 mL preservative-free 0.9% sodium chloride injection, USF. Load 0.5mL in a single syringe with a 30-gauge needle. Each of the five FDA approved injection points will receive 0.1 mL of the reconstituted solution (4 unit of toxin) intramuscularly for a total of 20 units in 0.5mL.

### OnabotulinumtoxinA (Botox) and IncobotulinumtoxinA (Xeomin)

Reconstitute 50 unit vials with 1.25 mL preservative-free 0.9% sodium chloride injection, USF. Load 0.5mL in a single syringe with a 30-gauge needle. Each of the five FDA approved injection points will receive 0.1 mL of the reconstituted solution (4 unit of toxin) intramuscularly for a total of 20 units in 0.5mL

### AbobotulinumtoxinA (Dysport)

Reconstitute 300 unit vials with 3.0 mL preservative-free 0.9% sodium chloride injection, USP. Load 0.5mL in a single syringe with a 30-gauge needle. Each of the five FDA approved glabella injection points will receive 0.1mL of the reconstituted solution (10 units of toxin) intramuscularly for a total of 50 units in 0.5mL.

Once reconstituted, unused toxin may be stored in the original container in a refrigerator at 2-8°C or 36-46°F. Do NOT freeze. All toxin must be discarded within 24 hours after reconstitution. All reconstituted vials should be single-use for one subject only.

### 5.2.2 Visit 2

Visit 2 which will occur 3-days post-injection, will consist of a repeat of the above measurements using 3D imaging with facial animations of 1) relaxed and 2) frowning. Subjects will also complete the FACE-Q via electronic REDCap survey and communicate any questions or concerns.

### 5.2.3 Visit 3

Visit 3 which will occur 30-days post-injection, will consist of a repeat of the above measurements using 3D imaging with facial animations of 1) relaxed and 2) frowning. Subjects will also complete the FACE-Q via electronic REDCap survey and communicate any questions or concerns.

#### 5.2.4 Visit 4

Visit 4 which will occur 90-days post-injection, will consist of a repeat of the above measurements using 3D imaging with facial animations of 1) relaxed and 2) frowning. Subjects will also complete the FACE-Q via electronic REDCap survey and communicate any questions or concerns.

#### 5.2.5 End of Study Visit 5

Visit 5 which will occur 180-days post-injection, will consist of a repeat of the above measurements using 3D imaging with facial animations of 1) relaxed and 2) frowning. Subjects will also complete the FACE-Q via electronic REDCap survey and communicate any questions or concerns.

**TABLE 1 SCHEDULE OF STUDY PROCEDURES**

	Baseline Visit 1	Intervention	Follow-up Visit 2 Day 3	Follow-up Visit 3 Day 30	Follow-up Visit 4 Day 90	Follow-up Visit 5 Day 180
Visit Window	Day 1	Day 1	Day 3 ±1	Day 30 ± 5	Day 90 ±7	Day 180 ±10
Eligibility	X					
Informed Consent	X					
Demographic	X					
Medical History	X					
Consultation	X					
Vectra Photography		X	X	X	X	X
FACE-Q		X	X	X	X	X
Adverse Events	X	X	X	X	X	X

#### 5.3 *Unscheduled Visits*

Unscheduled visits will be handled on a case by case basis dependent upon the reasoning for the patients' visit. If subjects are displaying signs of immediate danger or instability, they will be referred to emergency department or directly admitted. However, unscheduled visits are rare for this type of procedure.

#### 5.4 *Subject Withdrawal*

Subjects may withdraw from the study at any time without impact to their care. They may also be discontinued from the study at the discretion of the Investigator. Subjects may also be withdrawn following an adverse event that does not allow them to continue with the study. It will be documented

CONFIDENTIAL

whether or not each subject completes the study. Subjects who withdraw early will have one final communication to collect final evaluations and assess for adverse events.

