#### **5.4.1 Data Collection and Follow-up for Withdrawn Subjects**

Patients must document in a letter asking not to use the data collected and formalize the withdrawal. Otherwise, data up until withdrawal will be available for analysis.

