### **6 Statistical Plan**

#### **6.1 Sample Size and Power Determination**

The sample size is based on a previously successful study with the same purpose [1], and an anticipated 15% drop-out/withdrawal rate. Significant decrease in the dynamic strain in OnabotulinumtoxinA and AbobotulinumtoxinA were determined at day 4, 14, and 90 post intervention compared to baseline. We are increasing the patient population to account for a potential increase drop out due to the number of follow-up visits.

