### 7.2 Recording of Adverse Events

At each contact with the subject, the investigator will seek information on adverse events by specific questioning and, as appropriate, by examination. Information on all adverse events will be recorded immediately in the source document, and also in the appropriate adverse event module of the case report form (CRF). All clearly related signs, symptoms, and abnormal diagnostic procedures results should be recorded in the source document, though should be grouped under one diagnosis.

All adverse events occurring during the study period will be recorded. The clinical course of each event will be followed until resolution, stabilization, or until it has been determined that the study intervention

or participation is not the cause. Serious adverse events that are still ongoing at the end of the study period will be followed up to determine the final outcome. Any serious adverse event that occurs after the study period and is considered to be possibly related to the study intervention or study participation will be recorded and reported immediately.

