#### ***7.4.1 Follow-up report***

If an SAE has not resolved at the time of the initial report and new information arises that changes the investigator's assessment of the event, a follow-up report including all relevant new or reassessed information (e.g., concomitant medication, medical history) should be submitted to the IRB. The investigator is responsible for ensuring that all SAE are followed until either resolved or stable.

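### After the single Day 1 injection, discontinuation under Section 5.4 ends observation, not exposure; no later data collection is planned, and 5.4 is not reconciled with adverse-event follow-up in 7.2 and 7.4.1

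*Combined protocol and SAP*

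**What the plan says.** Treatment is given once. Section 4.1 states: "Subjects will receive injections on day-1, and follow up imaging and analysis occurs on day 3, 30, 90 and 180 post intervention". Table 1 schedules imaging, FACE-Q and adverse-event questions at each of the four follow-up visits.

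Section 5.4 gives three routes out of the study: the subject's own choice, the investigator's discretion, and adverse events. On the last it says: "Subjects may also be withdrawn following an adverse event that does not allow them to continue with the study". It then plans a single closing step: "Subjects who withdraw early will have one final communication to collect final evaluations and assess for adverse events". Section 5.4.1 covers data already held. A subject may ask by letter that they not be used; "Otherwise, data up until withdrawal will be available for analysis". Section 5.5 is headed as dealing with early termination visits, but it lists no imaging or other assessment.

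On safety, Section 7.2 says: "The clinical course of each event will be followed until resolution, stabilization, or until it has been determined that the study intervention" (the sentence goes on to include study participation) is not the cause. It adds: "Serious adverse events that are still ongoing at the end of the study period will be followed up to determine the final outcome". Section 7.4.1 says: "The investigator is responsible for ensuring that all SAE are followed until either resolved or stable". Neither 7.2 nor 7.4.1 mentions withdrawn subjects, and 5.4 refers to neither.

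**The concern.** In a trial with repeated dosing, taking a subject out after an adverse event may at least stop exposure. Here the dose has already been given. What remains is photography, a questionnaire and questions about adverse events, so discontinuation removes only information.

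Two things are at stake. The first is strain. The primary endpoint (3.4.1) is change in strain over time, and the primary objective (2.1) is a comparison of the four products. If subjects leave because of an event that the product caused, their later strain values are missing for a reason tied to treatment. Sections 6.2 and 6.3.2 name a paired t-test for continuous variables. A subject without a Day 90 or Day 180 image has no pair at that visit and leaves that test. Section 6 states no analysis set or missing-data method that would bring her back.

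The second is safety. Section 9.1 lists eyelid drooping, brow drooping and vision effects as risks. If such an event is still open when the subject leaves, site staff have one closing contact under 5.4 and an open-ended duty under 7.2, with nothing to say how the two fit together.

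**Working it through.** **The plan's own figure.** Section 4.2 gives 140 subjects and Section 6.1 a 15% drop-out allowance. The 140 cannot be rebuilt, because 6.1 gives no significance level, power, effect size or standard deviation. Only the drop-out step can be checked: 119 / 0.85 = 140, so 140 would fit a target of 119 completers, but 119 is not in the document. The point does not depend on this.

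**Expected losses, all causes.**
- Total: 140 × 0.15 = 21.
- Per arm, if spread evenly over four equal arms: 21 / 4 = 5.25 of 140 / 4 = 35, leaving 29.75.
- Share due to adverse events or investigator decision: not stated, so between 0 and 21.

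**Strain visits lost, by time of leaving** (follow-up images at Days 3, 30, 90 and 180):
- After the Day 3 image and before Day 30: Days 30, 90 and 180, or 3 of 4.
- After the Day 30 image: Days 90 and 180, or 2 of 4.
- After the Day 90 image: Day 180, or 1 of 4.

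Section 6.1 says of the earlier study: "Significant decrease in the dynamic strain in OnabotulinumtoxinA and AbobotulinumtoxinA were determined at day 4, 14, and 90 post intervention compared to baseline". For those two products at least, Day 90 is a visit at which a strain effect was still measurable.

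**An adverse event still open at discontinuation, section by section.**
- 5.4: one communication, which assesses adverse events and collects final evaluations. These are not defined and not said to include imaging.
- 5.4.1: the heading mentions follow-up of withdrawn subjects; the text covers only use of data already collected.
- 5.5: where the investigator decides, the subject is contacted and given the reasons; no assessment is listed.
- 7.2: every event is followed until it resolves, stabilizes or is found not to be caused by the study; ongoing serious events are followed to final outcome.
- 7.4.1: serious events are followed until resolved or stable.

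One contact cannot by itself follow an unresolved event to any of the end points in 7.2, and no section says which further contacts would do so.

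**Possible effect on strain (assumptions only).** If a fraction q of an arm is lost and the lost subjects differ from completers by D standard deviations (SD) in strain change, the completers' mean differs from the full-arm mean by q × D.
- q = 0.05, D = 0.25: 0.0125 SD.
- q = 0.10, D = 0.5: 0.05 SD.
- q = 0.15, D = 1.0: 0.15 SD.

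For a contrast between two arms with the same D, the shift is (difference in q) × D. It is zero if the loss rates are equal, and (0.15 − 0.05) × 1.0 = 0.10 SD with 15% against 5%. None of these values of q or D comes from the documents, and the top of the range needs all of the 15% drop-out to be event-related.

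**The case against.** The strongest reply is that a reader might infer that 5.4 caps follow-up at one contact and so contradicts 7.2. The text does not say that. Section 5.4 promises one communication without making it the last word on safety, and 7.2 covers each event with no exemption for withdrawn subjects. The sections can be read together as a closing contact for everyone plus continued follow-up of open events. That stands: this is an unreconciled ambiguity, not a proven contradiction.

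A reader might also infer that 7.2 drops non-serious events at the end of the study. Its general sentence has no time limit, and its sentence on serious events can be read as a stricter end point for those events. Section 7.7 also allows data collection for up to two years after treatment. So the documents do not show a cut-off, although they give no schedule for contacts after Day 180.

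Nor do the documents support saying that collected data are dropped: 5.4.1 keeps them by default, and the final communication adds to them. What has no provision is the later scheduled imaging, FACE-Q and adverse-event collection.

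It can be said that the closing-contact sentence concerns subjects who themselves withdraw, not those whom the investigator discontinues. The wording allows that reading, but it does not close the gap: the second group would then have no closing assessment beyond the explanation in 5.5.

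Finally, the Day 90 result is an efficacy finding for two of the four products and says nothing about how long adverse events last. The contrast between products is listed as secondary in 3.4.2, though 2.1 makes comparison the primary objective. Both remarks are fair, and neither removes the loss of later strain values.

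**Conclusion.** The concern holds as a gap in data collection and an unreconciled set of sections. Because the injection is given once, discontinuation after an adverse event or by investigator decision saves no exposure and forgoes between one and three of the four follow-up strain images once the Day 3 image has been taken. It may also leave the outcome of an unresolved event unrecorded, if staff treat the closing contact in 5.4 as the end of follow-up.

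The number affected is at most about 21 of 140 at the planned drop-out rate, or about 5 per arm if evenly spread. A reader might take the 21 as adverse-event withdrawals. The 15% is an all-cause figure, and 6.1 links possible extra drop-out to the number of visits, so 21 is an upper bound and the true number may be small. The size and direction of any bias are unknown; the range of about 0.01 to 0.15 SD in an arm mean is illustrative. Any bias between products further requires that event-related losses, or the subjects lost, differ by product.

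The change is worth making before enrolment because uncollected images cannot be recovered at analysis. It is not a reason to doubt the design as a whole.

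**What to change.** In 5.4, separate withdrawal of consent from discontinuation by the investigator or because of an adverse event. For the latter, state that the remaining Day 30, 90 and 180 data collection continues unless the subject withdraws consent: imaging where she is willing and able, otherwise FACE-Q and adverse-event questions by REDCap or phone. FACE-Q already goes out by REDCap after Visit 1 (7.7), and 7.6 already asks staff to seek limited later information even from subjects who revoke authorization.

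Reconcile 5.4, 5.4.1, 5.5, 7.2 and 7.4.1 so that they say the same thing about adverse events still open at withdrawal or at Day 180, serious or not, and say what the final evaluations in 5.4 consist of. Which follow-up rule governs is for the sponsor and investigator to decide.

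The cost is wording in these sections and a few extra contacts for at most about 21 subjects. The change reduces missing strain data but does not replace a stated missing-data method, which is a separate matter for Section 6.
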